**Education Time Influence on Exercise-Induced Hypoalgesia**

**NCT05658224**

**7/10/23**

## Procedures

Following informed consent and screening for inclusion/exclusion criteria, participants were randomly assigned into two groups. These groups consisted of a short educational group (SEG), in which participants were provided 1 minute of education on EIH before performing the activity, or a long education group (LEG) who were given 10-15 minutes of education on EIH before performing the activity. The SEG and LEG scripts are provided below in Appendices 1 and 2.

After group allotment, participant demographic information was collected. Demographic information of interest included age, gender, history of injuries, athletic participation history, and Knowledge and Beliefs about Exercise and Pain Questionnaire (KBAEPQ) (questions 1-5). Education and data collection were performed by the same two personnel for every round of participants, while the other two investigators, who were blinded to group allotment, were responsible for testing. After demographic data collection and education were provided, testing personnel were brought into the treatment room to introduce PPT. Hand-held algometers were used to assess PPTs, which was initially done on the participant's first web space, between the thumb and index finger, of the dominant hand. The algometer, which has a small, 1cm^2 probe, was applied perpendicular to the participant's skin. Pressure was applied with an increasing rate of 1kg of force per second until the pressure turned to pain. A verbal command was given by the participant to cue the tester to stop applying pressure and record the PPT measurement. After the initial introduction of PPT was delivered, baseline PPTs were delivered to the dominant quadriceps, 15 cm from the base of the patella and to the non-dominant upper trapezius muscle 10 cm proximal to the acromion, in line with the 7th vertebra. Determining the dominant limb was done by asking what hand a participant writes with and what leg would they use to kick a

ball. Before starting the wall squat, participants were asked to rate the pain in their legs using the NPRS ranging from 0 (no pain at all) to 10 (the worst pain imaginable). After baseline PPTs were measured and pain in the legs was recorded, participants were instructed to perform an isometric wall squat. The wall squat exercise consisted of standing upright with the participant's back against the wall with feet 45 cm from the wall, feet parallel and shoulder width apart, and hands at their side. Participants were then instructed to slide down the wall bending at the hips and knees, keeping their back against the wall and feet in place until their knee joint angle reaches 100 degrees of flexion, which was measured by the study personnel. A picture of the isometric wall squat was provided to the participants for familiarization. Participants were then asked to hold the wall squat position until fatigue or up to 3 minutes, whichever came first. Additional NPRS and RPE values were assessed by study personnel at the 1-, 2-, and 3-minute marks. The NPRS and RPE have been identified as having good reliability and validity in many different clinical trials. Immediately following cessation of the wall squat, PPTs were measured again in the dominant quadriceps and the non-dominant trapezius muscles. All PPTs were assessed 3 times with no less than 15 seconds in between. The average of the three trials was utilized for data analysis. Lastly, participants were asked to rate their expectation of exercise on PPTs using a -10 to 10 expectation scale. A score of -10 would indicate that much less pressure is needed to reach the PPT, a score of 0 indicates no change, and a score of 10 would indicate that much more pressure is needed to reach the PPT.

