## **Data Analysis**

All statistics will be performed using IBM SPSS Statistics for Windows, version 27.0 (IBM Corp., Armonk, N.Y., USA) using the significance threshold of  $\alpha < 0.05$ . Descriptive statistics of means, standard deviations, and frequencies will be calculated for the sample participants. An

independent samples t-test was calculated to compare differences between PPT at the two locations sites for the SEG and LEG before and after exercise as well as the change in PPT from the exercise. NPRS and RPE will be reported for each group with an independent sample t-test performed between groups.

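### Demographics and KBAEPQ belief items are taken after allotment by staff not described as blinded, and no pre-education value enters any between-arm comparison; precision is forgone, but validity is not lost

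*Combined protocol and SAP*

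**What the plan says.** All references are to the combined protocol and SAP.

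**Order of events (Procedures).** Screening comes first, then allocation: "Following informed consent and screening for inclusion/exclusion criteria, participants were randomly assigned into two groups". The next paragraph opens: "After group allotment, participant demographic information was collected". The items of interest are "age, gender, history of injuries, athletic participation history, and Knowledge and Beliefs about Exercise and Pain Questionnaire (KBAEPQ) (questions 1-5".

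**Who does what (Procedures).** "Education and data collection were performed by the same two personnel for every round of participants". Blinding is claimed only for the remaining staff: "the other two investigators, who were blinded to group allotment, were responsible for testing".

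**When the outcome measures start (Procedures).** "After demographic data collection and education were provided, testing personnel were brought into the treatment room to introduce PPT". The first PPTs used as baseline come after that introduction. The pre-squat leg-pain rating (NPRS) is also described after the education. RPE is described only during the squat, at 1, 2 and 3 minutes, and the expectation rating comes at the end of the session.

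**Analysis (Data Analysis).** Descriptive statistics are planned for the sample. For PPT before exercise, after exercise and as a change, an "independent samples t-test was calculated", and the same type of test is planned for NPRS and RPE. No covariate is named for any comparison.

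**The concern.** In most trials with a continuous outcome, the pre-intervention value of that outcome is the natural covariate. Here it does not exist: the PPT labelled baseline is already post-education, so an effect of education on the pre-exercise threshold would be contained in it, and RPE has no starting value at all. That leaves age, gender, injury history, athletic history and KBAEPQ as the only described data that could serve as pre-education covariates.

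Two features weaken their use. First, they are gathered after allotment by the people who then deliver the arm's education. For a self-reported belief questionnaire, in a trial whose intervention is education about exercise and pain, the way it is presented could shift the answers. Second, the planned tests use none of them. At stake are the precision of the arm differences and the credibility of the one belief measure that appears to come before the education.

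**Working it through.** **Step 1: sequence.** Setting the Procedures sentences side by side gives: consent and screening; random assignment; demographics and KBAEPQ; education; testers enter; PPT introduction; first PPTs and pre-squat NPRS; squat with NPRS and RPE; repeat PPTs; expectation rating. The place of demographics before education is inferred from the order in which the two are named; no sentence states it. Screening also precedes allotment, but its content is not described.

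**Step 2: which items could be affected.**
- Age and gender cannot change because a collector knows the arm.
- Athletic history is unlikely to change. Recalled injury history is somewhat more open to influence.
- KBAEPQ items are beliefs and are the plausible target.

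The text does not say that the collectors know the arm at the moment of collection. They deliver arm-specific education, allotment has already happened, and nothing is described that would shield them, so knowledge is probable.

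**Step 3: precision forgone.** The plan has no figure to reproduce: it states no sample size, SD or correlation. The following is an illustration. Let N be the total number of participants in two equal arms (assumed 40 or 60), k the number of covariates, and R² the share of within-arm outcome variance they explain (assumed 0 to 0.3). The expected ratio of the adjusted to the unadjusted standard error is approximately

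SE ratio = √[(1 − R²) × (1 + k/(N − k − 3))].

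The second factor is the average price of estimating k covariate slopes when the arms differ by chance on those covariates.

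- k = 1, N = 40: factor 1 + 1/36 = 1.028
- k = 1, N = 60: factor 1 + 1/56 = 1.018
- k = 2, N = 40: factor 1 + 2/35 = 1.057
- k = 2, N = 60: factor 1 + 2/55 = 1.036

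| k | N | R² = 0 | R² = 0.1 | R² = 0.2 | R² = 0.3 |
|---|---|---|---|---|---|
| 1 | 40 | 1.014 | 0.962 | 0.907 | 0.848 |
| 1 | 60 | 1.009 | 0.957 | 0.902 | 0.844 |
| 2 | 40 | 1.028 | 0.975 | 0.920 | 0.860 |
| 2 | 60 | 1.018 | 0.966 | 0.911 | 0.852 |

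So the standard error rises by 0.9% to 2.8% if the covariates explain nothing, and falls by 2.5% to 15.6% over R² = 0.1 to 0.3. With gender alone, adjustment breaks even when R² = 1 − 1/1.028 = 0.027 at N = 40, or 1 − 1/1.018 = 0.018 at N = 60.

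**Step 4: change scores.** If gender has the same covariance c with pre-exercise and post-exercise PPT, its covariance with the change is c − c = 0, and adjustment gains nothing. The table's right-hand columns are therefore more plausible for the pre- and post-exercise levels than for the change.

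**The case against.** The strongest reply is that nothing in the plan is invalid. Assignment is random, the t-test's standard error already allows for chance imbalance, and choosing an adjusted model is an optional improvement. That stands.

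A reader might infer that clean baseline covariates have been lost. The documents do not support this: the values are collected, apparently before the education, and stay available for analysis. Late collection cannot alter age or gender. A reader might also infer that imbalance in gender or prior belief biases the unadjusted arm differences. Under random assignment it adds variability, which the standard error reflects.

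A second reply concerns the remedy. If KBAEPQ answers did respond to the arm, adjusting for them could bias a comparison that is unbiased without them. Moreover, the documents mention only questions 1-5, with no scoring and no statement that the items form a total. Both parts stand and limit the model to gender unless those conditions are met.

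Third, the Procedures are written in the past tense and the Data Analysis section mixes tenses, so enrolment may be closed and reordering may help no one. This cannot be settled from the text. It makes the reordering conditional, but leaves the added model available, since gender is already recorded.

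Finally, the gain is not demonstrated, because the sample size and R² are assumed. That also stands; the figures show scale only.

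**Conclusion.** The point holds as a modest improvement to design and analysis. Demographics and KBAEPQ are taken after allotment by staff who are not described as blinded and probably know the arm, and no pre-education value is used in any between-arm comparison. The consequence is possible loss of precision, plus a belief measure whose independence from the arm cannot be assured. The unadjusted t-tests remain valid randomised comparisons.

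The size is illustrative: a cost of about 1-3% in standard error at worst, against a reduction of roughly 3-15% if the covariates explain 10-30% of the variance, probably less for the change in PPT. This rests on an assumed N of 40-60, equal arms, one or two covariates and the assumed R² range. It also rests on the implied, unstated order of demographics before education. Calling these items the only pre-education data is safe only for what the documents describe, since the content of screening is not given.

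**What to change.** 1. **Collection.** For any participants still to be enrolled, take demographics and KBAEPQ questions 1-5 between screening and allotment, and record from which participant the order changed. This reorders existing steps and adds no measurement.

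2. **Analysis.** Add a linear model with arm and gender for PPT (pre-exercise, post-exercise and change, at each site) and for RPE. Report the adjusted arm difference with its 95% confidence interval beside the unadjusted t-test. Fix the model before outcomes are examined; if they have already been seen, label it post hoc. The cost is analysis wording and, with gender alone, about 1% in standard error if gender is unrelated to the outcome (0.9% at N = 60, 1.4% at N = 40, both assumed).

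3. **KBAEPQ.** Add it as a covariate only where it was taken before allotment and its scoring has been defined in advance. Do not adjust for KBAEPQ values taken after allotment; report those descriptively by arm, with the timing and the collectors' role stated.

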## **Data Analysis**

All statistics will be performed using IBM SPSS Statistics for Windows, version 27.0 (IBM Corp., Armonk, N.Y., USA) using the significance threshold of  $\alpha < 0.05$ . Descriptive statistics of means, standard deviations, and frequencies will be calculated for the sample participants. An

independent samples t-test was calculated to compare differences between PPT at the two locations sites for the SEG and LEG before and after exercise as well as the change in PPT from the exercise. NPRS and RPE will be reported for each group with an independent sample t-test performed between groups.
